Title:

Clinical Evaluation of Enamel Microhardness Using At-Home and In-Office Tooth Whitening Agents

NCT#

07165366

Statistical Analysis:

April 21. 2024

Statistical Analysis

Microhardness was summarized for each active treatment group and for the negative and positive controls. Microhardness comparisons for the treatments and negative controls were performed using ANOVA, with a fixed effect for treatment and a random effect to account for within-subject correlations. Pair-wise tests between treatments were performed using the Sidak method to control the overall significance level. Shade change was summarized by treatment and compared between treatments using Wilcoxon Signed Rank tests (at-home versus in-office) and Wilcoxon Rank Sum tests (at-home with versus without PF). A two-sided overall 5% significance level was used.

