The methodology described in detail in field number 14 is summarized. The four premolars due to be extracted for orthodontic reasons will have at least a 1 x 1 millimeter surface flattened with a 169L bur. That surface will be polished with fine and extra fine sandpaper discs. This will improve the evaluation in the dental laboratory, especially of Vickers hardness. A maxillary premolar will be whitened at home with Opalescence 10% CP with PF in 30 sets of subjects and in 10 sets with Opalescence 10% CP without PF for 14 nights. The opposite maxillary premolar will be used as a control (no treatment). The mandibular and collateral premolar of the one that was whitened At-Home it will be whitened in all 40 sets at the office with Opalescent Boost PF 40% HP for a total of 60 minutes (three consecutive times of 20 minutes each). The opposite mandibular premolar to the control in three of the 30 sets of premolars that were treated with PF and in three of the 10 sets of premolars that were bleached without PF will have two narrow bands of Block-Out resin placed on a premolar. The area between the bands will be etched for 15 seconds with Ultra-Etch, a 35% phosphoric acid on the day of the extraction appointment. The extractions will be accomplished 14 days after finishing the whitening At-Home and In-Office procedures. The collected samples will be delivered to TTI for evaluation.

The *in-vivo* treatment of the teeth and the extractions will be performed at UIC. Treatment effects will be evaluated at TTI in Zionsville, Indiana, USA.

7- Keywords:

Demineralization, Teeth whitening, Profilometer, Scanning electron microscope (SEM), Vickers hardness, *in-vivo*.

8- INTRODUCTION OF THE PROJECT:

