At the first appointment (selection appointment), the absence of evident cavities or restorations in the four premolars will be clinically verified with an intraoral mirror. Root formation will be confirmed with the panoramic radiograph from the patient's orthodontic chart. The treatment will be explained, and the patient will be allowed to ask questions and discuss any concerns. Subjects will be informed that the study will consist of 4 appointments. If the patient qualifies and agrees to be part of the study, they will be asked to sign an approved Consent Form. Parents or guardians will be asked to sign the consent form for patients under 18 years of age. They will be given a copy of the signed Consent Form. The requirements are that the four teeth that will be extracted for orthodontic reasons will be flattened and polished to produce a one-by-one millimeter surface on the facial or most prominent surface. This will be done with a finishing carbide bur and fine and extra-fine sandpaper discs. Additionally, they must agree to use a whitening tray every night for 14 nights with Opalescence 10% CP with or without PF (potassium nitrate and fluoride) on an upper right premolar (UR) or on the upper left premolar (UL) (the tooth that has the best alignment). The contralateral lower right (LR) or lower left (LL) premolar will be treated with 40% hydrogen peroxide (HP) Opalescence Boost PF at the dental clinic for three 20minute periods according to the manufacturer's instructions**. Thirty of the 40 subjects will treat their UR or UL premolar treated with Opalescence 10% CP with PF. The remaining 10 subjects will treat the UR or UL premolar, with Opalescence 10% CP without PF.

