The third appointment will occur on day 15. The subject will return the maxillary whitening tray and will be encouraged to report any concerns with the bleaching treatment or tray usage. During this appointment, the LR or LL premolar and collateral to the one that was bleached at-home will be isolated with OpalDam (Ultradent Products, Inc.) and will be treated with Opalescence Boost PF 40%. The treatment will consist of the application of the gel three separate times, each will remain on the one premolar for 20 minutes, according to the manufacturer's instructions*. If the soft tissue or tooth is sensitive, a soothing gel will be applied to relieve discomfort (Opalescence UltraEZ). Tissue sensitivity usually lasts about thirty minutes and tooth sensitivity usually decreases in two or three days. This appointment will last approximately 90 minutes. During this appointment, an orthodontic separator band or elastic band of 2.5 to 4.5 oz / $\frac{1}{8}$ " to $\frac{1}{4}$ " (depending on interproximal access) will be placed in the gingival area of each premolar to create bone resorption and facilitate an atraumatic extraction. The final color will be taken of the premolar that received 14 days of whitening at-home, as well as the initial and final color of the premolar that will be bleached in-office with VITA Bleachedguide 3-D Master (VITA, Zahnfabrik, Germany); this is to corroborate and document that the teeth were successfully whitened. At this appointment, the subject will be reminded to complete the blood tests required by the UIC oral surgery department since, without these lab tests, the extractions cannot be performed. Therefore, the compensation would not be completed. Also, the subject will be reminded to

continue documenting on the log the brushing at least twice a day for at least one minute each time and will be asked to follow these instructions for the next 14 days.

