The fourth and final appointment will take place on day 29, in other words, 14 days after the third appointment and 14 days after they have already finished their whitening treatment at-home and in-office. At this appointment, 6 subjects, three of the 30 subjects that used 10% CP with PF and three of the 10 subjects that used 10% CP without the PF, will have their mandibular second control tooth etched with 35% phosphoric acid (Ultradent Products, Inc.) for 15 seconds. These 6 subjects will be chosen to be treated before extractions with the etchant at a time convenient to the oral surgeon and [name]. Extractions will be performed during this appointment for all subjects. Four to five UIC maxillofacial surgeons will perform the extractions. Local anesthetics will be at the discretion of the oral surgeon and the patient's needs. Extractions will be performed with a simple elevator forceps technique as described in the attached protocol**. Immediately after extractions, the teeth will be cleaned to remove any debris with a dental curette without touching the treated area. Each tooth will be placed in a miniature vial with hinged cap (ColePalmer) with a wet sponge (sodium-free drinking water) and 0.12% chlorhexidine at the bottom of the bottle and snapped closed. Each vial will be labeled with the date of extraction, a subject identification number, the subject's initials, the tooth number, and how the tooth was treated (at home, in-office, etching, or control) and forwarded for testing to Therametric Technologies, Inc.

*Instructions for in-office whitening Opalescent Boost PF 40% HP are attached.

**Extraction protocol is attached.

Research risks, data collection instruments in addition to the ethical aspects of the research:

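### At-home gel is always on an upper premolar and in-office gel always on a lower one, so the planned at-home versus in-office hardness test cannot separate product from arch

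*SAP*

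**What the plan says.** **Layout.** Protocol section 6 (General Summary) states: "A maxillary premolar will be whitened at home with Opalescence 10% CP with PF in 30 sets of subjects". Section 14 adds: "The remaining 10 subjects will treat the UR or UL premolar, with Opalescence 10% CP without PF". In-office 40% HP is used in all 40 subjects; section 14 (third appointment) describes that tooth as "the LR or LL premolar and collateral to the one that was bleached at-home". Only the side of the at-home tooth varies, and it is chosen by alignment. Section 14 also words the side of the in-office tooth inconsistently, but its arch is always the lower.

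**Controls.** In the upper arch, section 6 says: "The opposite maxillary premolar will be used as a control (no treatment". In the lower arch, section 14 (fourth appointment) says that six subjects "will have their mandibular second control tooth etched with 35% phosphoric acid". The other 34 lower teeth of this kind appear to stay untreated, although the protocol does not say so outright.

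**Analysis.** The SAP model for hardness is an ANOVA "with a fixed effect for treatment and a random effect to account for within-subject correlations", applied to the treatments and the negative controls. Then: "Pair-wise tests between treatments were performed using the Sidak method to control the overall significance level". There is no term for arch or tooth position. The SAP does not say how many pairs are tested, or whether upper and lower negative controls are one level or two.

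**The concern.** Product and arch coincide among the treated teeth. A random subject effect removes differences between mouths, but the upper-lower difference lies inside each mouth and stays in the product contrast. If upper and lower enamel differ in hardness, that difference would be reported as a difference between the at-home and in-office products, or it could mask a real one.

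The main objective (Protocol section 11) is whether whitening changes hardness, that is, treated versus untreated. That comparison is safe only if each product is set against the untreated tooth in its own arch. The SAP leaves this open. If the controls are pooled, arch bias enters the main comparison too, in opposite directions for the at-home and in-office products.

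**Working it through.** The documents give no SD, arch difference, correlation or power calculation for hardness, so there is no stated figure to reproduce. The check uses the planned layout and states its assumptions.

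**1. Teeth entering the model** (etched teeth excluded, because the SAP compares treatments and negative controls):

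| Group | Upper | Lower |
|---|---|---|
| CP with PF | 30 | 0 |
| CP without PF | 10 | 0 |
| In-office HP | 0 | 40 |
| Negative control | 40 | 40 − 6 = 34 |

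Total: 30 + 10 + 40 + 40 + 34 = 154.

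**2. Can arch be separated?** With treated teeth alone, three treatment columns plus an arch column have rank 3, so arch and product are fully aliased. With controls from both arches, four treatment columns plus arch have rank 5, so an additive arch effect can be estimated. If the controls are already two levels, an arch term adds nothing (rank stays 5).

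**3. Bias.** Let d be mandibular minus maxillary hardness in SD units. For a contrast L, the bias is L(X′V⁻¹X)⁻¹X′V⁻¹a × d, where X holds the treatment columns, a marks lower teeth, and V has unit variance and a common within-subject correlation. At correlation 0.5:

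| Contrast | Controls pooled | Controls separate |
|---|---|---|
| CP with PF − HP | −1.008d | −1.000d |
| CP with PF − control | −0.459d | 0 (upper control) |
| CP without PF − control | −0.425d | 0 (upper control) |
| HP − control | +0.550d | 0 (lower control) |
| CP with PF − CP without PF | −0.034d | 0 |
| Difference of same-arch differences | – | 0 |

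A hand check on the pooled column at zero correlation: 34/74 of the controls are lower, giving −34/74 = −0.459 for CP with PF and +40/74 = +0.541 for HP.

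**4. False-positive rates with no true treatment difference.** The Sidak level is 1 − 0.95^(1/k). For k = 6 (four levels, all pairs) it is 0.85%. For k = 10 (five levels) it is 0.51%. Rates come from the noncentral t with noncentrality bias/SE. For CP with PF versus HP, pooled, at d = 0.3: 1.008 × 0.3 / 0.174 = 1.74.

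| Contrast and reading (correlation 0.5) | d = 0.1 | d = 0.3 | d = 0.5 |
|---|---|---|---|
| CP with PF vs HP, pooled, six pairs | 2.0% | 17.9% | 58.7% |
| CP with PF vs HP, separate, ten pairs | 1.3% | 13% | 51% |
| CP without PF vs HP, pooled, six pairs | 1.3% | 5.9% | 19.7% |
| CP with PF vs pooled control, six pairs | 1% | 4% | 12% |
| HP vs pooled control, six pairs | 1% | 7% | 25% |

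Over correlations 0.3 to 0.7 the first row runs 2–3%, 12–34% and 42–85%. It reaches 5% at d = 0.17 (0.13 to 0.20 for correlation 0.7 to 0.3).

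**5. Simulation check.** In 20,000 REML fits at correlation 0.5 and the 0.85% level, CP with PF versus HP gave 2.0%, 16.8% and 54.5% with pooled controls, and 2.1%, 17.3% and 57.9% with separate controls. At d = 0.5 with pooled controls the simulated rate is somewhat below the noncentral-t figure. The difference of same-arch differences stayed at 0.8%, 0.8% and 0.9%.

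**The case against.** The case for giving this less weight has four parts.

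- **The contrast is not an objective.** The protocol asks about treated versus untreated enamel, and the SAP names at-home versus in-office only for shade. For hardness it arises from the general pairwise testing. This is true, and it limits the severity. But those tests are planned, the SAP title names both kinds of agent, and the result would be read as a product comparison.
- **The main comparison may be unaffected.** If the controls are two levels, each product against its own-arch control is free of this bias. That is correct, but the SAP does not say so. The vial label in Protocol section 14 records "the tooth number, and how the tooth was treated (at home, in-office, etching, or control", with one control category for both arches, so pooling is a live reading.
- **The size of d is assumed.** Nothing in the documents supports 0.3 or 0.5 SD. At 0.1 SD the worst rate is 2%, and CP without PF versus HP is affected much less often than CP with PF versus HP. All of this stands. Equally, nothing supports d = 0: flattening and polishing four teeth to one specification standardises the preparation, not the enamel. The lower rates for CP without PF reflect ten subjects rather than a smaller bias.
- **The remedy has limits.** It assumes that arch does not modify the treatment effect, which cannot be tested because each product is used in one arch. It also relies on 34 lower controls that are inferred. Both points stand and should be stated in the SAP.

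**Conclusion.** The concern holds. The aliasing follows from the layout and the model, and needs no assumed figure: the at-home versus in-office hardness contrast carries about 1.0d under either reading of the controls. Its practical effect depends on d, which is unknown. It is nil at d = 0; at correlation 0.5 with six pairs, the CP with PF versus HP false-positive rate is 2% at 0.1 SD, 18% at 0.3 SD and 59% at 0.5 SD, against a nominal 0.85%. The effect on the main treated-versus-untreated comparisons is conditional: 0.43d to 0.55d in absolute size if controls are pooled, zero if each product is compared with its own-arch control. The with-PF versus without-PF contrast is essentially unaffected.

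This should be fixed. The trial already collects what is needed to remove an additive arch effect, and the SAP as written does not ensure that it is used. The pooled-control figures, and the lower-arch part of the remedy, assume that the 34 unetched lower controls are measured as negative controls.

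**What to change.** Amend the SAP as follows.

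1. State that upper and lower negative controls are separate levels. Pooling them and adding a fixed arch effect is the same model. Confirm that the 34 unetched lower control teeth are measured as negative controls.
2. Define the main contrasts as CP with PF versus maxillary control, CP without PF versus maxillary control, and HP versus mandibular control.
3. Report at-home versus in-office hardness only as the difference between the two same-arch differences, for CP with PF and for CP without PF. State that this assumes no arch-by-treatment interaction and that the design cannot test it.
4. Keep CP with PF versus CP without PF. The family is then 3 + 2 + 1 = 6 comparisons, with a Sidak level of 1 − 0.95^(1/6) = 0.85%.

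**Cost.** A few lines and no new data, because tooth number and treatment are on each vial label. Precision falls relative to the pooled model. At correlation 0.5 the standard errors in SD units go from 0.156 to 0.174 for CP with PF versus control (about 11%), from 0.139 to 0.167 for HP versus control (about 20%), and from 0.174 to 0.242 for CP with PF versus HP (about 39%). If the SAP already intended separate control levels, only the last increase applies.

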The second appointment will occur at least 24 hours after the first appointment. The subject will receive the maxillary whitening tray with a single reservoir for the UR or UL premolar, a tube of Opalescence 10% CP containing or not containing PF whitening gel, and a container for tray storage, when tray is not in use. The tray will be placed in the mouth to ensure a proper fit without interference. During this appointment, the color of that premolar will be taken with VITA Bleachedguide 3-D MASTER shade guide (VITA, Zahnfabrik, Germany). The tray will be placed in the mouth to ensure a proper fit without interference. The subject will be instructed to place a small amount of whitening gel into the individual reservoir for the UR or UL premolar each evening, then carefully place the tray over the teeth, and wipe off the excess gel. The subject will be instructed to wear the bleaching tray for at least 8 hours every night, for 14 days, after brushing their teeth. Each morning after using the tray, the subject will be instructed to brush off the used gel, rinse the tray, store it in the container provided, and brush their teeth with the toothpaste provided. During the 14 days of whitening at home, the subject will be contacted twice by phone or text message to make sure they are using the tray with the whitening gel properly.

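### The with-PF versus without-PF shade comparison (30 v 10) makes no adjustment for the recorded initial shade: a minor loss of precision on a supportive outcome

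*SAP*

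**What the plan says.** The SAP's one paragraph on analysis covers shade in a single sentence, which opens: "Shade change was summarized by treatment and compared between treatments". For the paired contrast within subjects, the test named is "Wilcoxon Signed Rank tests (at-home versus in-office"). For the contrast between the two PF groups, it is "Wilcoxon Rank Sum tests (at-home with versus without PF"). It names no covariate, stratification or sensitivity analysis for initial shade. On error control it says "A two-sided overall 5% significance level was used".

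The protocol (section 14, Treatment plan) sets the group sizes. For the larger group: "Thirty of the 40 subjects will treat their UR or UL premolar treated with Opalescence 10% CP with PF". For the smaller group: "The remaining 10 subjects will treat the UR or UL premolar, with Opalescence 10% CP without PF".

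Initial shade is available. For the at-home tooth it is taken at the second appointment: "During this appointment, the color of that premolar will be taken with VITA Bleachedguide 3-D MASTER shade guide". Its final shade is taken at the third appointment. The in-office tooth is covered at that same visit: "as well as the initial and final color of the premolar that will be bleached in-office".

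The protocol gives the purpose of these readings as confirming that whitening took place. The main objective (section 11) is microhardness. The secondary objectives (section 12) are profilometry, SEM and the effect of PF judged from questionnaires and microhardness. Shade appears in neither section.

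**The concern.** A change score subtracts the initial shade, which is not the same as adjusting for it. Subtraction fixes the baseline coefficient at one, whatever the data say. If change still depends on where the tooth started, two things follow. That dependence is plausible on a shade guide, because a darker tooth has more steps to gain before the lightest tab.

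First, the part of the variation in change that initial shade could explain stays in the error term. With only 10 subjects on one side, that precision is worth having.

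Second, a difference in initial shade between the PF groups passes partly into the comparison of change, where it can imitate or mask a PF effect. The protocol text describes no random assignment to PF. The only subjects it calls randomly chosen are the six for etching (section 17). Balance at baseline therefore cannot be presumed.

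At stake is how well the trial can say whether PF alters whitening. The microhardness result is not involved.

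**Working it through.** **Inputs.** From the documents: n = 30 with PF, n = 10 without PF, two-sided 5%. The SAP gives no power, effect size, SD or correlation for shade, so there is no planned figure to reproduce. Assumed: the size r of the correlation between shade change and initial shade, taken as 0.3, 0.5 and 0.7.

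**Step 1: precision.** Adjusting for initial shade leaves a fraction 1 − r² of the variance of change:
- r = 0.3: 1 − 0.09 = 0.91
- r = 0.5: 1 − 0.25 = 0.75
- r = 0.7: 1 − 0.49 = 0.51

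The cost of estimating one covariate is a factor of about 1 + 1/36 = 1.03.

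If initial and final shade have equal SDs and correlation rho, then r = √((1 − rho)/2), so rho = 1 − 2r². The three cases correspond to rho = 0.82, 0.50 and 0.02. The last needs almost no correlation between initial and final shade, unless whitening also narrows the spread of final shades. It is the favourable end of the range.

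**Step 2: power.** Simulation at 30 v 10, shade in whole steps with an SD of 2 steps, PF effect of 1 SD of change, no systematic baseline difference:

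| r | Rank-sum on change | Rank ANCOVA |
|---|---|---|
| 0.3 | 72–73% | about 75% |
| 0.5 | 72–73% | about 82% |
| 0.7 | 72–73% | about 92% |

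**Step 3: level of the planned test.** With no PF effect and groups exchangeable at baseline, the rank-sum test rejects between 4% and just over 5% of the time. It keeps its nominal level.

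**Step 4: how much imbalance is carried over.** Under random assignment, the difference in mean initial shade has standard error √(1/30 + 1/10) = 0.365 SD, so about 95% of chance differences lie within 1.96 × 0.365 = 0.72 SD. When change depends on starting shade with equal SDs, a baseline difference D shifts the contrast in change by −(1 − rho)D: −0.8D, −0.5D and −0.2D at rho = 0.2, 0.5 and 0.8. Only part of the imbalance is carried.

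If the groups differ systematically and PF has no effect, the simulated rejection rates are:

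| r | Rank-sum, D = 0.5 SD | Rank-sum, D = 1 SD | Rank ANCOVA, either D |
|---|---|---|---|
| 0.3 | 6% | 12% | about 5% |
| 0.5 | 10% | 25% | about 5% |
| 0.7 | 15% | 43% | about 5% |

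**Step 5: the opposite data-generating assumption.** Suppose true shade differs between groups, both groups whiten equally, and change tracks initial shade only because readings contain error. With reliability λ, r = √((1 − λ)/2), which is 0.39 at λ = 0.7 and 0.50 at λ = 0.5. With no PF effect:

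| Reliability | D | Rank-sum | Rank ANCOVA |
|---|---|---|---|
| 0.7 | 0.5 SD | 4.5% | 8.6% |
| 0.7 | 1 SD | 5.2% | 16.3% |
| 0.5 | 0.5 SD | 4.7% | 10.5% |
| 0.5 | 1 SD | 4.6% | 23.9% |

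Steps 4 and 5 share similar values of r and reach opposite conclusions about which test is biased. The documents do not say which assumption is nearer the truth.

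**The case against.** The strongest reply is that a rank-sum test on change is a conventional, valid analysis of ordinal shade scores, applied to an outcome that serves only to confirm that whitening occurred. Most of this stands. The test holds its level under exchangeability (step 3). The imbalances of 0.5 and 1 SD in step 4 are not typical of chance: with a standard error of 0.365, chance alone exceeds 0.5 SD about 17% of the time and 1 SD about 0.6%. The gain in power is unknown and is only 2 to 3 points at r = 0.3.

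Step 5 also stands. If the groups differ systematically, choosing between a change score and baseline adjustment is a choice between assumptions, and adjustment is not a guaranteed cure.

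What the reply does not remove is the precision point. Where the groups are exchangeable, adjusting for a baseline already in hand costs almost nothing and may gain up to about 20 points of power. The SAP did choose to test PF on shade, and the smaller group has 10 subjects.

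A reader might also extend the criticism to the at-home versus in-office comparison, since it sets an upper against a lower premolar. That test is paired within subject, and the documents offer nothing from which to size a loss, so the point is not made here.

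**Conclusion.** The planned PF shade test is valid if the groups are exchangeable at baseline, but less efficient than it could be. For a 1-SD effect at 30 v 10, power of about 72–73% would become about 75%, 82% or 92% with baseline adjustment at r = 0.3, 0.5 or 0.7. These correlations are assumptions, and the simulated figures are indicative. The test also carries part of a baseline shade difference into its result if change truly depends on starting shade. This matters more because no randomised PF assignment is described.

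Three stronger readings are not supported:
- **That the SAP ignores initial shade.** The change score uses it. What is missing is adjustment.
- **That the rank-sum test is wrong or inflates false positives in general.** It does so only under systematic imbalance combined with a real dependence of change on starting shade.
- **That an adjusted test would always stay near 5%.** Step 5 shows rejection rates of about 9% to 24% under reading error.

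This is a minor efficiency improvement on a supportive outcome. No stated objective rests on it.

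**What to change.** In the SAP:

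1. Add a baseline-adjusted comparison of at-home whitening with and without PF. Use rank ANCOVA of shade with initial shade as covariate. If an adjusted difference with a 95% CI is wanted, use linear ANCOVA on the ordered shade score, because rank ANCOVA does not give a difference on the shade scale.
2. Tabulate initial shade by PF group.
3. Report the Wilcoxon rank-sum test alongside.
4. State how disagreement will be read. If the two analyses differ because initial shade differs between the groups, interpret the PF shade result with caution and do not treat the adjusted result as the correction.

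The cost is a few lines of SAP text and code and one model degree of freedom. No new data are needed. The SAP is written in the past tense, so if shade has already been analysed, the added comparison should be labelled post hoc.
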